Comparisons of the primary endpoint, change in HbA1c levels from randomization, between canagliflozin and placebo groups will be performed using analysis of covariance models. Since the correlation between baseline levels of HbA1c and change in the measure at 6 months is not presently well known, power calculations are based on use of two-sample t-tests, which assume similarity of the two randomized groups on HbA1c at baseline. Enrollment of 36 patients is planned. Assuming use of a two-sided t-tests with a significance level of 0.05, and that variability in HbA1c change at 6 months is similar to that seen at 1 year in Cefalu et al. (2013) [SD=0.9%], there will be 80% power to detect mean differences of 1.0% in HbA1c change between groups with enrollment of 22 patients in the canagliflozin group and 11 in the placebo group. Power calculations were performed using SAS software (Version 9.4; Cary, NC). If we assume dropout of 10%, and enroll 24 patients in the canagliflozin group and 12 in the placebo group, this should allow for adequate power despite the expected loss to follow-up. Since analysis of covariance models will provide increased

power relative to t-tests in the presence of positive correlation (Borm et al, 2007), the effect size that can be detected is conservatively large.

Nutritional assessment for vitamin/mineral deficiency will be performed per clinical care guidelines(46) at the screening visit. Subjects will be asked to take nutritional supplements (i.e. vitamins and minerals) per current clinical guidelines for post-bariatric patients. Stable doses of supplements will be established for at least 2 weeks prior to randomization. Thirty-six subjects with recurrent diabetes that are naïve to hypoglycemic agents with HbA1c greater than or equal to 6.5% and less than 11% will be randomly assigned to a six month course of a) canagliflozin 100mg for 2 weeks titrated up to 300 mg daily (N = 24) vs. placebo (n= 12) at the randomization. Patients taking an anti-diabetic medication will be asked to washout for 8 weeks prior to the randomization visit. At randomization, biochemical assessment of glycemic parameters (fasting glucose, HbA1c), lipid panel, complete metabolic panel, uric acid, leptin, total and HMW adiponectin, C-reactive protein and urine for albumin/creatinine ratio will be performed. DXA scan will be performed for body fat composition.

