Following randomization, subjects will be clinically evaluated at three office visits at 6 weeks, 3 and 6 months by PI and/or the research staff. The primary outcome measures at 6 months post-randomization include HbA1c followed by the change in HbA1c from randomization. Secondary measures include fasting glucose, BMI, change in body weight, blood pressure, lipid profile. Symptomatic hypoglycemia (blood glucose < 70) and drug related side effects (i.e. mycotic genital infections, urinary tract infection) will be monitored with adverse event reporting. Metabolic testing in all subjects at randomization and at 6

months will include a DXA scan for body fat composition and blood for leptin and adiponectin levels.

Rescue glucose lowering therapy will be provided for all subjects with a blood glucose >250 mg/dl. If chronic uncontrolled hyperglycemia (HbA1c $>11\%$) occurs then basal bolus insulin will be implemented. Subjects (20-75 years) who underwent AB, SG or RYGB within the past 15-years will be recruited. Including subjects who underwent surgery within the past 15-years will broaden the subject pool, as additional subjects who initially remitted and were subsequently rediagnosed will be identified. However, we will prioritize subjects who underwent metabolic surgery ≤ 6 years ago and who initially achieved remission status documented by HbA1c of $\leq 6.5\%$ within first year and a subsequent glycated hemoglobin $\geq 7.5\%$ (without any hypoglycemic agents) and less than 11% as upper limit. The rationale to prioritize patients that initially remit is that these patients have demonstrated ability to respond to surgical weight loss and subsequently redeveloped the disease. Whereas those that never achieved initial remission status may not respond to any intervention due to inexorable beta cell failure.

Initial recruitment will be achieved by a general awareness campaign, which will emphasize a study of methods of diabetes management post metabolic surgery. All patients will be pre-screened for inclusion and exclusion criteria by our clinical trial research nurse coordinator and/or research fellow. Evaluation of the inclusion and exclusion criteria, which are listed below, will occur both at the initial screening visit and the baseline visit, prior to randomization.

Statistical Methods

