Visit 3: Randomization visit with research coordinator and PI: Review of eligibility. Labs will be drawn for HbA1c, fasting glucose, lipid panel, uric acid, complete metabolic panel and adipokines (C-reactive protein, leptin, total and HMW adiponectin, leptin). Urine for albumin/creatinine ratio. DXA scan will be performed for body composition at this visit. Blood and urine will be collected for the bio-repository collection and is optional.

Visit 4: 6 week f/u visit: Research fellow/coordinator to assess adherence and safety.

Visit 5: 3 month visit with research coordinator and PI: Review of clinical status and biochemical labs will be drawn. These will include HbA1c and a complete metabolic panel.

Visit 6: 6 month visit with research coordinator and PI: Review of clinical status and biochemical labs will be drawn. These include HbA1c, fasting glucose, lipid panel, uric acid, complete metabolic panel and uric acid. Urine for albumin/creatinine ratio. Additionally, a DXA scan for body composition and blood for adipokines (C-reactive protein, total and HMW adiponectin, leptin) will be performed. Blood and urine will be collected for the bio-repository collection and is optional.

The window for all visits will be +/- 4 weeks.

Research Team: [name] is the principal investigator of this study and will consult with [name] (bariatric surgeon) for enrollment of appropriate candidates who underwent metabolic surgery at any Cleveland Clinic location, but that live within two hours of the Cleveland Clinic Main Campus. Both investigators have a long standing,

productive relationship. Statistical analysis will be provided by a Cleveland Clinic Quantitative Health Sciences statistician dedicated to endocrine and diabetes research. This team is well qualified to run post-bariatric trials and have successfully run two randomized control trial of bariatric vs. medical therapy for type 2 diabetes in obese patients.

POSSIBLE RISKS

Risks associated with Canagliflozin Include:

All drugs can cause unwanted effects called side effects. As of 28 September 2015 approximately 13173 subjects have received canagliflozin in completed or ongoing studies of 12 weeks or longer.

Side effects found in these studies that are more likely to occur with canagliflozin include those below. You should speak with your doctor about any changes to your diet or other medications you are taking:

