If you are able to have children and you are heterosexually active, you must use birth control (contraception) during the study. Birth control methods that can be used while in this study include: avoiding sex, birth control pills, birth control injections or patch, intrauterine device, barrier method (for example, condoms or diaphragm) combined with spermicide (foam, cream, or gel), or your male partner is sterile (e.g. sperm tubes are cut or blocked). The type of birth control you use must be discussed with the study doctor before you begin the study. The study doctor must approve the method you use before you can enter the study.

If you become pregnant during the study, you must tell the doctor immediately. You will have to stop taking the study drug. The doctor will advise you about your medical care and will ask you to allow him/her to collect information about your pregnancy and the health of your baby.

For male subjects, if your partner becomes pregnant, you must tell the study doctor immediately.

Adverse event reporting:

I. Management of Safety Data

This Study has been designated as an interventional study. Janssen requirements for IIS interventional studies are all adverse events regardless of causality and special situations excluding those from subjects not exposed to a Janssen Medicinal Product and product quality complaints with or without an adverse event will be reported, once the subject has signed and dated an Informed Consent Form is obtained until the subject has completed participation in the study and for 30 days after the last dose of study drug.

II. Definitions

a. Adverse Event (AE)

An adverse event is any untoward medical occurrence in a clinical study subject administered a medicinal (investigational or non-investigational) product. An adverse event does not necessarily have a causal relationship with the treatment. An adverse event can therefore be any unfavorable and unintended sign (including an abnormal finding), symptom, or disease temporally associated with the use of a medicinal (investigational or non-investigational) product, whether or not related to that medicinal (investigational or non-investigational) product. (Definition per International Conference on Harmonisation [ICH]).

This includes any occurrence that is new in onset or aggravated in severity or frequency from the baseline condition, or abnormal results of diagnostic procedures, including laboratory test abnormalities.

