- Results in persistent or significant disability/incapacity
- Is a congenital anomaly/birth defect
- Is a suspected transmission of any infectious agent via a medicinal product
- Is medically important*

*Medical and scientific judgment should be exercised in deciding whether expedited reporting is also appropriate in other situations, such as important medical events that may not be immediately life threatening or result in death or hospitalization but may jeopardize the subject or may require intervention to prevent one of the other outcomes listed in the definition above. These should usually be considered serious.

NOTE: DEATH FOR ANY REASON SHOULD BE REPORTED AS A SERIOUS ADVERSE EVENT.

For reports of hospitalization, it is the sign, symptom or diagnosis which led to the hospitalization that is the serious event for which details must be provided.

Any event requiring in-patient hospital admission (or the prolongation of hospitalization) must be reported as an SAE. Events that do not meet the criteria for SAE reporting are:

- Reasons described in the Protocol, e.g. drug administration, Protocol-required testing
- Social reasons, e.g. overnight stay because of distance between home and hospital
- Surgery or procedure planned and documented prior to entry into the Study.

Any event requiring hospitalization or prolongation of hospitalization that occurs during the study must be reported as a serious adverse event, except hospitalizations for the following:

- Hospitalizations not intended to treat an acute illness or adverse event (e.g., social reasons such as pending placement in long-term care facility)
- Surgery or procedure planned before entry into the study. [Note: Hospitalizations that were planned before the start of data collection and where the underlying condition for which the hospitalization was planned has not worsened will not be considered serious adverse events. Any adverse event that results in a prolongation of the originally planned hospitalization is to be reported as a new serious adverse event.]

The cause of death of a subject in a study within 30 days of the last dose of study drug, whether or not the event is expected or associated with the study drug, is considered a serious adverse event.

f. Unlisted (Unexpected) Adverse Event/Reference Safety Information

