V. Management of Hypoglycemic Events

The management of hypoglycemia defined as blood glucose <70 mg/dl with symptoms or requiring assistance will be implemented with oral glucose tablets or juice. The use of canagliflozin alone is typically not associated with hypoglycemia.

VI. Pregnancy

All initial reports of pregnancy must be reported to Janssen Scientific Affairs by the Sponsor Investigator **within 24 hours of their awareness of the event** using the Serious Adverse Event Form. Abnormal pregnancy outcomes (e.g. spontaneous abortion, stillbirth, and congenital anomaly) are considered serious adverse events and must be reported using the Serious Adverse Event Form.

Any subject who becomes pregnant during the study must be promptly withdrawn from the study and discontinue further study treatment.

Because the effect of the Janssen medicinal product on sperm is unknown, pregnancies in partners of male subjects exposed to a Janssen medicinal product will be reported by the Sponsor Investigator **within 24 hours of their awareness of the event** using the Serious Adverse Event Form. Depending on local legislation this may require prior consent of the partner.

Follow-up information regarding the outcome of the pregnancy and any postnatal sequelae in the infant will be required.

VII. Reporting Procedures for Adverse Events and Pregnancies [and/or Pregnancies in Partners]

All adverse events, whether serious or non-serious, related or not related, special situations, pregnancy exposures and/or pregnancies in partners following exposure to a Janssen medicinal product are to be documented by the investigator and recorded in the CRF and in the subject's source records. Investigators must record in the CRF their opinion concerning the relationship of the adverse event to a Janssen medicinal product.

All (serious and non-serious) adverse events reported for a Janssen medicinal product should be followed-up in accordance with clinical practice.

All serious adverse events that have not resolved by the end of the study, or that have not resolved upon discontinuation of the subject's participation in the study, must be followed until any of the following occurs:

- The event resolves
- The event stabilizes
- The event returns to baseline, if a baseline value/status is available
- The event can be attributed to agents other than the study drug or to factors unrelated to study conduct

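### Adverse events are reportable for 30 days after the last dose, but for subjects who complete treatment, stop shortly before Visit 6 or leave the study on stopping, no scheduled contact covers that whole window

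*Combined protocol and SAP*

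**What the plan says.** Under Adverse event reporting, I. Management of Safety Data, all adverse events regardless of causality are to be reported from signed consent "until the subject has completed participation in the study and for 30 days after the last dose of study drug". Section II.e adds that "The cause of death of a subject in a study within 30 days of the last dose of study drug" counts as a serious adverse event, whether or not it is expected or linked to the drug.

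The treatment and visit plan is given under Sample Size Considerations and under the visit schedule:

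- Subjects "will be randomly assigned to a six month course of" canagliflozin or placebo.
- After randomization, "subjects will be clinically evaluated at three office visits at 6 weeks, 3 and 6 months".
- The final entry in the schedule is "Visit 6: 6 month visit with research coordinator and PI: Review of clinical status and biochemical labs will be drawn". No visit, call or other contact is listed after it, and there is no early-termination visit.
- "The window for all visits will be +/- 4 weeks".

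Section VII deals with events once they are known. "All serious adverse events that have not resolved by the end of the study", or by discontinuation, must be followed to an endpoint, and "adverse events reported for a Janssen medicinal product should be followed-up in accordance with clinical practice".

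**The concern.** The protocol sets a safety window that its own schedule does not observe for most subjects. Section VII follows events that have already come to light; it does not create an occasion on which new ones would be asked about. The duty to report serious events within 24 hours starts when the site becomes aware of them, so it depends on the site learning of them in the first place.

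What is at stake is how completely safety events are found in the month after treatment ends. The Possible Risks section names events that would belong in that record if they occurred, including fractures, urinary infections that spread, and ketoacidosis.

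**Working it through.** The plan gives no figure of its own to reproduce, so the check compares the reporting window with the visit schedule by day count.

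**Inputs.** Reporting window after the last dose: 30 days (section I). Course length: six months (Sample Size Considerations). Last scheduled contact: Visit 6 at six months. Visit window: plus or minus 4 weeks, or 28 days. Assumption: six months is taken as 182 days and three months as 91 days.

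**Formula.** Let g be the number of days from the last dose to the last scheduled contact. Days of the window not covered = max(0, 30 − g).

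**Results by type of subject.**

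- *Completer, last dose on the day of Visit 6:* g = 0, so 30 − 0 = 30 days uncovered. If dosing always runs to the visit, this holds whatever the visit date.
- *Completer, drug stopped at exactly six months, Visit 6 at the late edge of its window:* g = 28, so 30 − 28 = 2 days uncovered. This is the most favorable permitted timing, and the protocol does not plan for it.
- *Subject who stops drug fewer than 30 days before Visit 6:* 30 − g is positive, so part of the window is uncovered. Stopping 10 days before, for example, leaves 30 − 10 = 20 days.
- *Subject who leaves the study on stopping drug:* no later contact is scheduled, so all 30 days are uncovered.
- *Subject who stops drug at Visit 5 (three months) and stays in the study:* nominally g = 182 − 91 = 91 days. With Visit 5 as late and Visit 6 as early as allowed, g = 91 − 28 − 28 = 35 days. Both exceed 30, so Visit 6 can cover the window in retrospect.

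**Share of calendar time.** For a completer with g = 0, the uncovered days are 30 / (182 + 30) = 30 / 212 = 14% of the post-randomization reporting period.

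**Likely number of events.** Possible Risks gives upper annual rates on canagliflozin of 1 in 50 for fracture and 1 in 150 for amputation. Assuming these on-drug rates persist after stopping, 24 canagliflozin subjects over 30 days give:

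- fractures: 24 × (30/365) × (1/50) = 0.04
- amputations: 24 × (30/365) × (1/150) = 0.013

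These are expected events in the window, and so upper limits on the expected number missed under those rates.

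**The case against.** The strongest reply is that the gap is narrow and that nothing in the planned analysis depends on it. Much of this stands, and it rules out several stronger readings that a reader might infer.

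- *That everyone who stops early is unobserved.* Not so. A fall in eGFR below 45 leads to withdrawal of study medication, not of the subject. A subject stopped at Visit 5 still has Visit 6 more than 30 days later.
- *That a subject withdrawn for pregnancy has no further contact.* The Pregnancy section requires follow-up of the outcome and the infant, and Possible Risks says the doctor will ask to collect that information. This contact is required but not dated in the schedule.
- *That the window rests only on spontaneous reports.* This is an inference. The document does not say how events in the window are to be found. Consent pages are not in the public copy and could tell subjects to report. The program's routine clinical follow-up is another possible route.
- *That the safety comparison is biased, or that unobserved days are counted as event-free.* Statistical Methods plans no person-time safety analysis. The schedule is the same in both arms of a double-blind trial, so no difference between arms is evident.
- *That 14% of events are missed.* The 14% is a share of calendar days. Intervals without a visit are normal: Visit 5 to Visit 6 is about 91 days. The difference is that a later visit can ask about that interval, whereas no visit follows the last 30 days.

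It can also be said that section I states the funder's reporting requirement and excludes events in subjects not exposed to its product. As placebo comes from the institution's pharmacy, the sentence may not reach placebo subjects. That is fair. The case for contacting both arms rests on blinding and equal ascertainment, not on that sentence.

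None of this supplies the missing contact for completers, for subjects who stop shortly before Visit 6, or for those who leave on stopping.

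**Conclusion.** The point holds for those three groups. For a completer, between 2 and 30 days of the 30-day window have no scheduled contact after them, and the figure is 30 if dosing runs to Visit 6. New events there may go undetected, because the follow-up rules apply only to events already known.

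The consequence is modest. The expected number of missed serious events in 36 subjects is small, and the six-month HbA1c comparison is unaffected. This is a low-cost improvement in safety ascertainment and not a threat to the trial's main conclusion.

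The conclusion assumes that the published visit schedule is complete and that the drug is taken for about six months. The event counts further assume that the document's on-drug rates carry over after stopping.

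**What to change.** Add one line to the visit schedule: a scripted telephone safety contact at or shortly after day 30 following the last dose, for example day 30 to 37. It applies to every subject whose 30-day window is not already covered by a later scheduled visit, including those who leave the study on stopping drug and agree to be called.

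- Use the same script and timing in both arms, so that blinding and ascertainment are preserved.
- Ask about any adverse event, hospitalization, fracture, infection and pregnancy, and record the answers on the adverse event page of the CRF.
- Define completion of safety follow-up as this contact, or as the later visit that covers the window. Section I does not define when participation is complete.
- State that, for subjects who stop earlier and remain in the study, the next visit falling at least 30 days after the last dose asks about the whole window.

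The cost is up to 36 short calls by existing staff, with last-subject completion about 30 days later. No dose or clinical rule changes.
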